4.3.2 Data Monitoring Committee

A Data Monitoring Committee (DMC) will be reviewing safety data on an ongoing basis. The DMC membership includes experienced clinicians and a statistician, all of whom have expertise in clinical studies. Further details are specified in the DMC Charter. The presentation and analysis of data for the DMC meetings will be described in a separate DMC SAP.

4.4 Multicenter studies

In general, the data from all centers will be pooled for the purposes of the analysis. However, the effect of center (using a pooling of centers by region) on results will be evaluated as mentioned in [Section 3.8](#).

4.5 Multiple comparisons/multiplicity

A step-down closed testing procedure will be applied for the primary endpoint and some secondary endpoints. The testing procedure will account for multiplicity and control the family-wise type I error rate at alpha=0.05 (2-sided).

For each test, on each binary efficacy endpoint, the null hypothesis is that the conditional odds ratio is equal to one ($H_0: OR_{T1T2} = 1$). The alternative hypothesis is that the conditional odds ratio is not equal to one ($H_A: OR_{T1T2} \neq 1$).

For each test, on each continuous efficacy endpoint, the null hypothesis is that there is no difference between treatment groups ($H_0: T_1 - T_2 = 0$). The alternative hypothesis is that there is a difference between treatment groups ($H_A: T_1 - T_2 \neq 0$).

T_1 refers to BKZ and T_2 to placebo.

According to this strategy, the statistical testing of an endpoint can be investigated only if the null hypothesis for the previous endpoint has been rejected (i.e., if $p < 0.05$). [Table 4-5](#) shows the testing order for these endpoints.

Table 4-5: Sequential testing procedure of primary/secondary efficacy endpoints (fixed sequence testing procedure) (All efficacy endpoints at Week 16)

BKZ 160mg Q4W	
H_1	ACR50 Response superior to Placebo
H_2	Change from Baseline HAQ-DI superior to Placebo

BKZ 160mg Q4W	
H ₃	PASI90 Response superior to Placebo
H ₄	Change from Baseline SF-36 PCS superior to Placebo
H ₅	MDA superior to Placebo
H ₆	Change from Baseline vdHmTSS* superior to Placebo on subjects with elevated hs-CRP and/or with at least one bone erosion (hs-CRP ≥ 6 mg/L and/or erosion-positive)
H ₇	Enthesitis-free state superior to Placebo (based on pooled PA0010 and PA0011 W16 data)
H ₈	Dactylitis-free state superior to Placebo (based on pooled PA0010 and PA0011 W16 data)
H ₉	Change from Baseline vdHmTSS** superior to Placebo

ACR=American College of Rheumatology; BKZ=bimekizumab; CfB=change from Baseline; H=hypothesis;

HAQ-DI=Health Assessment Questionnaire - Disability Index; hs-CRP=high sensitivity C-reactive protein;

LEI=Leeds Enthesitis Index; MDA=Minimal Disease Activity; PASI=Psoriasis Area and Severity Index.

PCS=Physical Component Summary; Q4W=every 4 weeks; SF-36=Short-Form 36-item Health Survey;

vdHmTSS=Van der Heijde modified Total Sharp Score.

* It is planned to enroll a minimum of 45% of subjects who are positive for elevated hs-CRP (hs-CRP ≥ 6 mg/L) and/or who have at least 1 bone erosion at Screening.

**Based on the overall population

4.6 Use of an efficacy subset of subjects

The RS will be the primary analysis set for efficacy analyses, but analyses will also be repeated on the FAS and the PPS for the primary efficacy endpoint. The FAS analysis will evaluate whether there are differences in the efficacy analysis between randomized subjects and randomized subjects with a Baseline assessment, while the PPS analysis will evaluate the effect of IPD on the analysis.

4.7 Active-control studies intended to show equivalence

Efficacy outcomes are based on superiority comparisons of the Bimekizumab 160mg sc Q4W to placebo, this section is then not applicable for this study.

4.8 Examination of subgroups

Subgroup analyses will be performed on the variables below. They are all assessed at Baseline except concomitant cDMARDs, concomitant MTX and ADA_b status which will be assessed during the 16-week DBP. Subgroup analyses will be performed on the ACR50 response, the PASI90 response and the HAQ-DI response (subjects with a decrease of HAQ-DI from Baseline of at least 0.35) at Week 16. ADA_b status will also be used for subgroup analysis for the PK endpoints. The variables for subgroup analyses will be:

- Age (<45 years of age, ≥ 45 years of age)
- Gender (male, female)
- Disease duration (<1 year, ≥ 1 year)

- Region (eg, North America, Western Europe, Eastern Europe, Asia. Western Europe will be combined with Asia if any of these 2 regions have less than 10% of the randomized subjects)
- Race (White, Black and Other)
- Body weight at Baseline ($\leq 100\text{kg}$, $>100\text{kg}$)
- Bone erosion (≥ 1) at Baseline (Yes, No)
- hs-CRP at Baseline ($<6\text{mg/L}$, $\geq 6\text{mg/L}$)
- Bone erosion (≥ 1) and/or hs-CRP $\geq 6\text{mg/L}$ at Baseline (Yes, No)
- Prior cDMARDs (0, 1, ≥ 2) (taken prior to Baseline,). Such medications will be classified using the adjudicated spreadsheet.
- Concomitantly receiving cDMARDs versus no concomitant cDMARDs
- Concomitantly receiving MTX versus no concomitant MTX
- Concomitantly receiving MTX at Baseline vs. other cDMARDs at Baseline (MTX at Baseline, no MTX at Baseline and cDMARDs at Baseline, no MTX at Baseline and no cDMARDs at Baseline)
- PSO affected BSA at Baseline ($<3\%$, $\geq 3\%$ to 10% , $>10\%$)
- BASDAI at Baseline (<4 , ≥ 4)
- ADAb status (positive, negative) ([Section 9.2](#)) (for the BKZ 160mg Q4W group only)
- Human leukocyte antigen B27 (HLA-B27) (positive, negative).

In the context of submission to Japanese health authorities, a subset of tables and figures will be provided in the subgroup of subjects randomized in Japan(when MI is used, data for subjects randomized in Japan will be extracted from the MI datasets generated for the full population).

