6.2.2 Other Baseline characteristics

The following variables will be summarized by treatment group and overall:

- Bone erosion (0, ≥ 1) – based on IXRS randomization strata
- Bone erosion (0, ≥ 1) – based on actual randomization strata (as per imaging data)
- Bone erosion (≥ 1) and/or hs-CRP ≥ 6 mg/L at Screening (Yes, No). To determine this, bone erosion will be derived from imaging data and corresponds to actual randomization strata
- % of BSA affected by PSO (<3%, $\geq 3\%$ to $\leq 10\%$, $>10\%$)
- PASI score at Baseline (for subjects with PSO involving at least 3% of BSA at Baseline). This variable will be summarized as a continuous variable and in classes (<10, 10 to 20, >20)
- BASDAI (<4, ≥ 4)
- Rheumatoid factor (positive, negative). A rheumatoid factor value <30 IU/mL is defined as negative and a value ≥ 30 IU/mL is defined as positive
- Anti-cyclic citrullinated peptide (CCP) antibodies (positive, negative). Anti-CCP antibodies negative is a value <20 U/mL and a value ≥ 20 U/mL is defined as positive
- Nail psoriasis (yes, no)
- Dactylitis (“yes” if LDI score >0 , “no” if LDI score = 0, missing)
- Enthesitis based on LEI (“yes” if LEI score >0 , “no” if LEI score = 0, missing)
- Enthesitis based on SPARCC (“yes” if SPARCC >0 , “no” if SPARCC = 0, missing)
- Prior NSAID (yes, no)
- NSAID at Baseline (yes, no)
- Past cDMARDs therapy (yes, no)
- Prior cDMARDs (0, 1, ≥ 2) ([Section 4.8](#))
- cDMARDs at Baseline (yes, no)
- HLA-B27 (positive, negative)
- Methotrexate at Baseline (yes, no) ([Section 4.8](#))
- Prior oral corticosteroids (yes, no)
- Oral corticosteroids at Baseline (yes, no).

To understand the study population during the different periods of the COVID-19 pandemic, the reporting of other Baseline characteristics will be repeated by COVID-19 period (pre or during as determined by the Baseline visit date) on the SS.

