6.4 Prior and concomitant medications

Prior medications include any medications that started prior to the date of the first IMP administration.

Concomitant medications are medications taken at least one day in common with the IMP dosing period.

The IMP dosing period corresponding to the combined DBP and ATP will be calculated as follows:

The study medication dosing period start date is defined as the date of first dose.

The study medication dosing period stop date is defined as follows:

- For subjects who are ongoing at the time of the clinical data cut (not including participants who are in SFU) use date of last clinical contact
- For subjects who died prior to last visit (not including those who died during SFU), use the minimum of the following:
 - Date of death
 - Date of last dose of any study medication + 28 days
- For subjects who complete the study as planned, the dosing period ends at the later of the following 2 dates:
 - Date of last administration of IMP + 14 days
 - The last scheduled visit date not including SFU
- For all other subjects, use the maximum of the following:
 - Date of last dose of any study medication + 28 days
 - Date of last visit (not including SFU).

In the case of missing data, the classification of medications as prior or concomitant will be performed as described in [Section 4.2.4](#). Imputations of missing data will be performed before calculation of relative study days.

The number and percentage of subjects taking prior medications (excluding past psoriasis medications) will be summarized on the SS by treatment group, overall and by ATC class, presenting Anatomical Main Group (ATC Level 1), Pharmacological Subgroup (ATC level 3) and PT.

The table summary will be ordered alphabetically for the ATC class and in terms of decreasing frequency for PT within ATC class in the BKZ treatment group. In the event of ties, PT will be ordered alphabetically.

The number and percentage of subjects taking concomitant medications will be summarized similarly on the SS by treatment group (for the Week 24 analysis on the period from Baseline to Week 24, for the Week 52 analysis on the overall study treatment period).

A by-subject listing of all prior (on the RS) and concomitant medications (on the RS) as well as glossary of all medical medications will be provided.

6.5 Prohibited medications and permitted rescue therapy after Week 16

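### SAP 4.8 defines the yes/no concomitant cDMARD and MTX subgroups by use during the 16-week treatment period; Baseline status, already derived, would keep the BKZ-placebo subgroup contrasts protected by randomization, though the likely bias is small

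*SAP*

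**What the plan says.** SAP Section 4.8 introduces the subgroup list with the sentence "They are all assessed at Baseline except concomitant cDMARDs, concomitant MTX" and ADAb "status which will be assessed during the 16-week DBP". The two entries concerned are "Concomitantly receiving cDMARDs versus no concomitant cDMARDs" and "Concomitantly receiving MTX versus no concomitant MTX". They apply to ACR50, PASI90 and HAQ-DI response at Week 16.

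Section 8.1.3 runs the ACR50 subgroup analyses on the RS. The logistic model contains treatment, the subgroup and their interaction. For each category the plan reports responder rates, the BKZ-placebo odds ratio and the difference, each with a 95% CI, and shows the odds ratios in a forest plot. Sections 8.2.3 and 8.3.1.19 carry the same method to PASI90 and HAQ-DI response.

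Baseline versions exist. Section 6.2.2 lists "cDMARDs at Baseline (yes, no") and "Methotrexate at Baseline (yes, no"). Section 4.8 also has a three-level subgroup that rests on Baseline use alone: "Concomitantly receiving MTX at Baseline vs. other cDMARDs at Baseline".

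Section 6.4 gives the only general definition: "Concomitant medications are medications taken at least one day in common with the IMP dosing period". That dosing period is the combined DBP and ATP, whereas Section 4.8 limits these subgroups to the DBP.

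**The concern.** A treatment comparison within a subgroup keeps the protection of randomization only if membership is fixed before treatment can influence it. Use during the DBP does not meet this condition. A subject who is not on a cDMARD at Baseline but starts one before Week 16 moves from the no-concomitant stratum to the concomitant stratum. If such starts depend on arm or on response, the two arms within a stratum are no longer comparable.

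The plan leaves room for this:

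- Section 3.5 foresees subjects who receive new prohibited medication for an adverse event.
- Section 4.2.2.5 foresees subjects who stop IMP but stay in the study, and Section 8.1.4.5 describes the compared regimens there as including other medication as needed.
- Under the NRI rule (Section 4.2.2.1), a subject who stops IMP before Week 16 is a non-responder. If that subject then starts a cDMARD or MTX during the DBP, a certain non-responder changes stratum.
- Section 8.1.2 deals with prohibited or rescue use through Week 16 only by means of the PPS analysis, so such subjects remain in the RS subgroup tables.

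At stake is the description of whether the BKZ effect depends on background therapy. The primary conclusion is not at stake.

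**Working it through.** **Is membership post-randomization?** Yes. Section 4.8 names these variables as exceptions to Baseline assessment and places them in the DBP, which starts at the first dose. ADAb status is also post-randomization, but it is limited to the BKZ arm with no placebo contrast, so it is not part of this point.

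**Inputs from the SAP (Section 2.4.1).** 420 BKZ and 280 placebo subjects; ACR50 rates of 43.8% and 16%; stated odds ratio 4.09.

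**The plan's own figure.** (0.438/0.562) / (0.16/0.84) = 0.7794/0.1905 = 4.09. It reproduces.

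**Assumptions that are not in the SAP.** The share *b* using the drug at Baseline; the share *s* of non-responding Baseline non-users who start it in the DBP, by arm; and the same true response rates in users and non-users, so the true ratio of odds ratios is 1.

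**Formula.** In an arm with response rate *p*, the share that starts is *m* = (1−*b*)(1−*p*)*s*. The observed response rate is *bp*/(*b*+*m*) in the concomitant stratum and (1−*b*)*p*/((1−*b*)−*m*) in the other.

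**Example, *b* = 0.6, *s* = 10% placebo and 3% BKZ.**

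- Placebo: *m* = 0.4 × 0.84 × 0.10 = 0.0336; rates 0.096/0.6336 = 15.2% and 0.064/0.3664 = 17.5%.
- BKZ: *m* = 0.4 × 0.562 × 0.03 = 0.0067; rates 0.2628/0.6067 = 43.3% and 0.1752/0.3933 = 44.6%.
- Odds ratios 4.28 (concomitant) and 3.80 (none); ratio 1.13.

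**Range over *b* = 0.5 to 0.7.**

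| Start share, placebo / BKZ | OR, concomitant | OR, none | Ratio of ORs |
|---|---|---|---|
| 0% / 0% | 4.09 | 4.09 | 1.00 |
| 2% / 1% | 4.11–4.13 | 4.05 | 1.01–1.02 |
| 5% / 2% | 4.14–4.21 | 3.97 | 1.04–1.06 |
| 10% / 3% | 4.21–4.37 | 3.80 | 1.11–1.15 |

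**One-sided case in whole subjects.** Take *b* = 0.6, so 112 placebo non-users with 17.92 responders and 168 users with 26.88. Let 8 placebo non-responders start and no BKZ subject. The placebo rates become 17.92/104 = 17.2% and 26.88/176 = 15.3%. The odds ratios are 0.7794/(17.92/86.08) = 3.74 and 0.7794/(26.88/149.12) = 4.32, a ratio of 1.15. Eight is 3% of the placebo arm, but 8/112 = 7.1% of its non-users and 8/94.08 = 8.5% of its non-responding non-users.

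**Against sampling error.** With 252 and 168 BKZ subjects in the strata, the variance of the log ratio of odds ratios is 1/(252×0.438×0.562) + 1/(168×0.438×0.562) + (1/26.88 + 1/149.12) + (1/17.92 + 1/86.08) = 0.016 + 0.024 + 0.044 + 0.067 = 0.152, so the SE is 0.39. The spurious log ratio is 0.144, or 0.37 SE. The 95% CI around 1.15 runs from about 0.54 to 2.48, and a 5% two-sided interaction test would reject about 6.6% of the time.

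**With Baseline status.** No one can change stratum after randomization, so both odds ratios stay at 4.09 and the ratio is 1.00.

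**The case against.** The strongest reply is that the design leaves little room for subjects to change stratum. Stable doses of permitted DMARDs are verified at Screening (Section 2.3.2.1), rescue is permitted only after Week 16 (Section 6.5), and prohibited or rescue use before then is an important deviation (Section 8.1.2). Nothing in the SAP gives a rate at which subjects start a cDMARD or MTX in the DBP. The larger ratios above need many starters, mostly or only on placebo and all non-responders. A starter who stays on IMP could respond, which could change the direction. This all stands, and it limits the size.

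It also stands that the three-level Baseline subgroup covers much of the same question: its first level against the other two is MTX at Baseline yes/no, and its first two against the third is any cDMARD at Baseline yes/no. The plan reports its three categories separately, however, so it is only a partial substitute for the two yes/no contrasts.

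Two stronger readings are tempting, and the document supports neither:

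- A reader might infer that the plan will produce a false interaction with background therapy. The working shows at most a small shift, well inside sampling error, and Section 8.1.3 lists no interaction p-value among its outputs.
- A reader might take the Section 6.4 overlap rule to mean that rescue after Week 16 defines these subgroups. Section 4.8 confines them to the DBP.

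**Conclusion.** The point holds as a minor one. The two yes/no subgroups are defined on a post-randomization variable while BKZ-placebo odds ratios and an interaction are fitted on the RS, so the estimates lack the protection of randomization. Under the assumed start rates and Baseline use, the spurious ratio of odds ratios lies between 1.00 and 1.15, and it is near 1.00 if few subjects start the drug, which the design makes plausible. These rates are assumptions; the SAP gives none.

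The analyses are outside the testing hierarchy in Section 4.5, so neither the primary result nor the type I error is affected. A clean alternative is already derived, and the amendment log (Amendment 2, Change #9) shows that the neighbouring three-level subgroup was itself moved from concomitant to Baseline MTX use. No stated reason supports keeping the other two on DBP use.

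**What to change.** In Section 4.8, define the two yes/no subgroups by cDMARDs at Baseline and methotrexate at Baseline, as derived in Section 6.2.2, for ACR50, PASI90 and HAQ-DI response. Amend the introductory sentence so that ADAb status is the only variable taken from the DBP. If use during the DBP is of interest, tabulate it by arm as descriptive information, without BKZ-placebo odds ratios within its categories.

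Section 3.10 lists the combined MTX/cDMARD subgroup as an addition to the protocol but not the two yes/no ones, which suggests that the protocol specifies the concomitant version. The protocol is not at hand; if it does, record the change in Section 3.10.

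The cost is a rerun of these subgroup tables and forest plots, and loss of direct comparability with any Week 24 version already produced. Sample size, power and alpha do not change.

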5 STUDY POPULATION CHARACTERISTICS

5.1 Subject disposition

Subject disposition will be summarized for all subjects screened overall, by region and by site. In this summary, the dates of first subject screened and dates of last subject last visit (end of the study), number of screened subjects, and the number of subjects included in each analysis set (RS, SS, FAS, AMS, ATS, PPS, RAS, PK-PPS, COVID-19-free Set) will be presented.

The disposition of subjects into treatment groups and analysis sets will also be summarized on the RS.

Reasons for screen failures (as collected on the Study Termination Screen Failure CRF page) will be listed for all screened subjects who failed to be randomized.

The number and percentage of randomized subjects who completed the study, completed the study not on randomized treatment, who discontinued IMP overall and by reason and who discontinued the study, with the primary reason for study discontinuation (as collected on the Study Termination CRF page), by study treatment period (DBP and ATP) will be tabulated

overall and by treatment group. The numbers and percentages of randomized subjects entering the SFU Period will additionally be presented. The numbers and percentages of these subjects who either complete the SFU visit or not will additionally be presented.

The numbers and percentages of randomized subjects entering the Open Label Extension (OLE) study and those not entering the OLE study will be presented. Of the randomized subjects not entering the OLE study.

A subject will be said to have completed the study if she/he had completed the last scheduled study visit, not including SFU visit (the SFU visit is typically 140 days after the last dose of IMP, which is roughly equivalent to 5 half-lives of BKZ).

A subject will be considered to have completed a period if she/he completes the last scheduled study visit for that period.

Subjects who previously discontinued IMP and are continuing for all scheduled visits through the end of each period (DBP or ATP) will also be considered as completing the period. A separate summary of subjects who discontinue IMP will be provided.

Finally, the number of randomized subjects who discontinued the study due to AEs (during the DBP and the ATP separately) by type of AEs (serious fatal, non-fatal, other) will be summarized.

Study disposition and termination details will be listed for all screened subjects. Additional listings will be created on study discontinuation, subject analysis sets and visit dates (both actual visit and visit remapped for analysis). A listing will also be provided for subjects who did not meet the study eligibility criteria.

To assess subject disposition (entry and periods in the study) during the COVID-19 pandemic, subject disposition will be assessed by period of the COVID-19 pandemic (pre – during) ([Section 3.11](#)), by comparing the dates of visits (or events) to the dates of the COVID-19 pandemic period.

5.2 Impact of COVID-19

A listing of visits affected by COVID-19 will be presented based on the Enrolled Set including the visit, dates of visit, relationship to COVID-19, impact category and a narrative (short description) of the event. These data will be summarized by treatment group and overall, for randomized subjects.

A summary of study visits by COVID-19 pandemic period (pre – during) will be presented for subjects enrolled prior or during the pandemic.

In addition, in order to assess the potential impact of COVID-19 on the collection and reporting of efficacy data, a separate summary based on the RS will be presented to display missing data as well as data collected via an alternative modality (eg: phone, video call) for efficacy endpoints included in the hierarchy ([Table 4-5](#)). For these displays, missing data will be presented only for visits affected by COVID-19, as reported on the dedicated eCRF page. Missing data at other visits and for other reasons will not be included.

For visits conducted remotely, it was not possible to assess some endpoints (eg, TJC, SJC, LDI, LEI, PASI, etc.) and therefore these assessments will be missing for those visits. In addition, for any missed visit or visit conducted remotely, the CRP assessment will also be missing. Such

assessments will be considered missing because of the COVID-19 pandemic. For these visits, it will therefore not be possible to assess composite endpoints like ACR response. For this summary table based on the RS, only visits at which efficacy assessments are scheduled will be included.

5.3 Protocol deviations

The definition of an IPD is given in [Section 3.5](#).

A summary displaying the number and percentage of subjects with an IPD will be provided by treatment group separately for the DBP on the RS and on the ATP on the ATS. This will include a summary of subjects excluded from the PPS (DBP only) and the PK-PPS. The summary will be provided overall and by type of deviation (inclusion criteria deviation, exclusion criteria deviation, withdrawal criteria deviation, prohibited concomitant medication, incorrect treatment or dose, treatment non-compliance, procedural non-compliance, COVID-19 related IPD) as well as the number and percentage of subjects excluded from the PPS due to reason other than PD.

Criteria for exclusion of subjects from the PPS or PK-PPS will be defined in a separate document.

A by-subject listing of IPDs will be provided for all subjects in the RS.

A by-subject listing of COVID-19 related PDs will be provided for all subjects in the RS.

A by-subject listing of subjects excluded from the PPS for reasons other than IPD will be provided.

